5.5.11 Withdrawal of informed consent

Subjects may voluntarily withdraw consent to participate in the study for any reason at any time. Withdrawal of consent occurs only when a subject:

- Does not want to participate in the study anymore, and
- Does not allow further collection of personal data

In this situation, the investigator should make a reasonable effort (e.g. telephone, e-mail, letter) to understand the primary reason for the subject's decision to withdraw his/her consent and record this information.

Study treatment must be discontinued and no further assessments conducted, and the data that would have been collected at subsequent visits will be considered missing.

Further attempts to contact the subject are not allowed unless safety findings require communicating or follow-up.

All efforts should be made to complete the assessments prior to study withdrawal. A final evaluation at the time of the subject's study withdrawal should be made as detailed in the assessment table.

Confidential

Novartis will continue to keep and use collected study information (including any data resulting from the analysis of a subject's samples until their time of withdrawal) according to applicable law.

All biological samples not yet analyzed at the time of withdrawal may still be used for further testing/analysis in accordance with the terms of this protocol and of the informed consent form.

5.5.12 Study completion and post-study treatment

Each patient will be required to complete the study in its entirety and thereafter no further study treatment will be made available to them. The study will complete when the last patient completes their Study Completion visit, and any repeat assessments associated with this visit have been documented and followed-up appropriately by the Investigator. After completion of the trial, each patient will be offered the opportunity to participate in a separate follow-up trial.

The investigator must provide follow-up medical care for all patients who are prematurely withdrawn from the study, or must refer them for appropriate ongoing care.

All patients will be expected to participate in a separate long term follow-up observational study.

5.5.13 Early study termination

The study can be terminated at any time for any reason by Novartis. Should this be necessary, the patient should be seen as soon as possible and treated as a prematurely withdrawn patient. The investigator may be informed of additional procedures to be followed in order to ensure that adequate consideration is given to the protection of the patient's interests. The investigator will be responsible for informing IRBs and/or ECs of the early termination of the trial.

6 Visit assessments

The full Assessment schedule is presented at the end of the synoptic section, above.

Patients should be seen for all visits on the designated day or as close to it as possible.

Patients who discontinue study before completing the study, and those who prematurely withdraw from the study for any reason, should be scheduled for a visit as soon as possible, at which time all of the assessments listed for the final visit will be performed.

Acceptable deviations ranges from assessment times based on logistical and operational considerations are detailed in separate data management module documents.

6.1 Dietary, fluid and other restrictions

During recruitment, screening/informed consent review, and baseline visit, the patients will be informed and reminded of the following restrictions:

Confidential

- Avoid strenuous physical exercise (e.g., weight training, aerobics, football) before each visit and until after Study Completion evaluation.
- Avoid alcohol for 48 hours before each visit until after Study Completion evaluation.
- Patients should avoid getting water into their external auditory canal for 2 weeks after surgery.
- Patients may not swim for 4 weeks after surgery.
- Patients may not be passengers in airplanes for 2 weeks after surgery.

All patients will fast prior to surgery as instructed in the surgical procedure manual and continue to fast for at least 4 hours thereafter.

6.2 Patient demographics / other baseline characteristics

Patient demographic and baseline characteristic data to be collected on all patients include: date of birth, age, sex, race, predominant ethnicity.

Relevant medical history/current medical conditions data includes data until signature of informed consent. Where possible, diagnoses and not symptoms will be recorded.

6.3 Treatment exposure and compliance

Not required.

6.4 Efficacy assessments

Efficacy/Pharmacodynamics will be measured in this clinical study by the following assessments:

Auditory assessments

- Pure tone audiometry
- Speech audiometry
- Brainstem auditory evoked response evaluations (BAER)

Vestibular assessments

• Head Impulse Test

6.4.1 Auditory assessments

6.4.1.1 Pure tone audiometry

Hearing sensitivity to frequency-specific pure tone stimuli will be determined by measuring audiometric thresholds through earphones (air conduction) and bone-conduction vibrator (bone conduction) using a standard loudness bracketing procedure. The patient will be asked to respond when s/he hears the tone, and the softest sound detected will be defined as threshold for that tone. Immittance testing is completed as part of standard audiometric assessment.

- Air conduction thresholds will be measured for standard-frequency and extended-frequency ranges: 0.125, 0.25, 0.5, 1, 2, 3, 4, 6, 8, 10, 12.5, 14, 16 kHz.
- Bone conduction will be measured for frequencies 0.25 -4 kHz. Masking to determine ear-specific bone conduction thresholds will be performed when necessary.

6.4.1.2 Speech audiometry

For all speech perception tests, the patient repeats the words and/or sentences after they are presented. Speech perception is scored in percent of words correctly repeated.

- Ear-specific speech recognition threshold (SRT) will be measured using two-syllable spondee words via monitored live voice through headphones. SRT is defined as the lowest stimulation level at which speech perception is 50% correct.
- Ear-specific word recognition at 40 dB sensation level (SL), or maximum comfortable level if 40 dB SL not possible, will be tested using NU-6 words via monitored live voice through headphones.
- Aided word recognition testing for individual ears using consonant-nucleus-consonant (CNC) words (Peterson and Lehiste 1962) will be presented at 60 dB SPL-A in the sound field. The CNC is a test of 50 monosyllable words, and the stimuli are a pre-recorded test of 50 monosyllabic words.

6.4.1.3 AzBio Sentence test

The Minimum Speech Test Battery (MSTB) for cochlear implant evaluation was updated in 2011 to include more challenging sentence test materials, such as the AzBio Sentences Test (Spahr and Dorman 2004), due to ceiling effects in performance observed with the Hearing in Noise Test (Gifford et al 2008). The AzBio Sentences Test consists of 15 sentence lists, with the MSTB including 8 additional lists, and is scored in percent of words correctly repeated. The AzBio sentence test presented at 60 dB SPL-A, both in quiet and with background 10-talker speech babble noise presented at +5 dB signal-to-noise-ratio (SNR). Presentation is in the soundfield in an individual-ear aided condition.

6.4.1.4 Hearing-in-Noise-Test (HINT)

The Hearing in Noise Test (HINT) (Nilsson et al 1994) consists of 25 lists of recorded sentences presented at 60 dB SPL-A in quiet and in speech-weighted noise at +8 SNR. The HINT sentences are relatively easy to understand and often show ceiling effects of performance with cochlear implant testing. For this reason, the cochlear implant test battery

has recently been updated to replace the HINT with the AzBio Sentences Test. However, the HINT can also be administered adaptively, with the sentences remaining at a fixed stimulation level and the noise level adapted until the patient scores 50% correct understanding. Performance is quantified as signal-to-noise ratio (SNR) in dB. This adaptive testing method avoids ceiling effects observed when using fixed stimulation levels; however, this method is not routinely used clinically in the US. One potential future benefit is it resembles adaptive sentence in noise testing in other languages, such as the German Oldenburger Satztest/Oldenburg Sentence Test (OLSA). Presentation is in the sound field in an individual-ear aided condition.

6.4.1.5 Brainstem auditory evoked response evaluations (BAER)

The BAER provides electrophysiologic information on the status of the auditory pathway from the periphery up through the brainstem. The BAER waveform reflects responses from different neural generators, with the most robust neural response arising from the inferior colliculus, observed as wave V. The BAER can be elicited by click or tone-burst stimuli, the latter providing more frequency-specific information.

Surface electrodes are placed as non-inverting on the vertex, inverting on lobe or mastoid of the test ear, and ground on the forehead. The patient is at rest, and the click or toneburst stimuli are presented through insert earphones at a high level (starting level depends on degree of hearing loss), and the stimulation level is decreased until BAER threshold is obtained, defined as the lowest stimulation level at which a repeatable wave V is observed.

6.4.2 Vestibular assessments

6.4.2.1 Head Impulse Testing

The head impulse test (HIT) is a clinical maneuver used to assess the vestibulo-ocular reflex (VOR) during quick head rotations. The examiner delivers small-amplitude (<20 degree) head rotations with high peak velocities in the planes corresponding to each of the six semicircular canals. (Halmagyi and Curthoys 1988, Cremer 1998). A normal VOR results in a smooth eye movement equal and opposite direction to the head movement, thus achieving gaze stabilization without the need of a compensatory eye saccade. A patient with a deficient VOR fails to keep his/her eyes on target and subsequently makes a corrective, quick eye movement (a corrective/catch-up saccade) to refixate the target. When this refixation saccade occurs after the head has come to rest at the end of the head movement, it is visible to an examiner and serves as an indicator of hypofunctional sensation in the semicircular canal predominantly excited by the head motion. Head impulses can be directed in each of 6 directions, thereby selectively testing the function of each of the 3 semicircular canals in each of the two labyrinths.

Over time, a patient with a hypofunctional semicircular canal may develop an ability to make corrective saccades that begin and end during the head rotation. While this improves the patient's ability to maintain visual fixation of a target during head movements, it also degrades the examiner's ability to detect hypofunction of the semicircular canal. In such cases, a video Head Impulse Test (vHIT) is useful to identify VOR abnormalities that are not obvious to the examiner. A vHIT system comprises an eye-tracking camera and motion sensor

Novartis	
Amended Protocol Version v06 (Clean)	

mounted on light, securely fit, head-worn goggles. Because the vHIT system's camera travels with the head, it is less susceptible to missing corrective saccades that occur during the head movement. Because the vHIT quantitatively measures head and eye angular velocities throughout a head movement, it provides a numerical estimation of VOR gain, which is calculated as the ratio of slow phase (VOR-driven) eye velocity divided by head velocity. The vHIT has been well validated against the magnetic field scleral search coil technique, which is the gold standard for HIT measurements (MacDougall et al 2013).

6.5 Safety

6.5.1 Physical examination

A complete physical examination will include the examination of general appearance, skin, neck (including thyroid), eyes, ears, nose, throat, lungs, heart, abdomen, back, lymph nodes, extremities, vascular and neurological. If indicated based on medical history and/or symptoms, rectal, external genitalia, breast, and/or pelvic exams may be performed.

Information for all physical examinations must be included in the source documentation at the study site and will not be recorded the CRF. Significant findings that are present prior to informed consent are included in the Relevant Medical History CRF. Significant findings observed after informed consent signature which meet the definition of an Adverse Event must be appropriately recorded on the Adverse Event CRF.

6.5.2 Vital signs

Vital signs include blood pressure (BP) and pulse measurements. After the patient has been sitting for 3 minutes, with back supported and both feet placed on the floor, systolic and diastolic BP will be measured using an automated validated device, with an appropriately sized cuff. In case the cuff sizes available are not large enough for the patient's arm circumference, a sphygmomanometer with an appropriately sized cuff may be used.

If vital signs are out-of-range at screening and baseline, the Investigator may obtain two additional readings, so that a total of up to three consecutive assessments are made, with the patient seated quietly for approximately five minutes preceding each repeat assessment.

6.5.3 Height and weight

Height in centimeters (cm) and body weight (to the nearest 0.1 kilogram [kg] in indoor clothing, but without shoes) will be measured.

Body mass index (BMI) will be calculated using the following formula:

• BMI = Body weight $(kg) / [Height (m)]^2$

6.5.4 Laboratory evaluations

In the case where a laboratory assessment that is listed in the inclusion/exclusion criteria is outside of a **protocol-specified range** at screening and/or at the initial baseline, the assessment may be repeated once prior to randomization. If the repeat value remains outside of protocol-specified ranges, the patient is excluded from the study.

In the case where a laboratory range is **not specified by the protocol**, but is outside the reference range for the laboratory at screening and/or initial baseline, a decision regarding whether the result is of clinical significance or not shall be made by the Investigator and shall be based, in part, upon the nature and degree of the observed abnormality. The assessment may be repeated once prior to randomization.

Further retests at screening or baseline could be permitted if deemed necessary by the investigator; however, each case must be discussed and agreed with the Sponsor on a case-by-case basis.

In all cases, the Investigator must document in the source documents, the clinical considerations (i.e., result was/was not clinically significant and/or medically relevant) in allowing or disallowing the patient to continue in the study.

Confidential

Clinically relevant deviations of laboratory test results occurring during or at completion of the study must be reported and discussed with Novartis personnel. The results should be evaluated for criteria defining an adverse event and reported as such if the criteria are met. Repeated evaluations are mandatory until normalization of the result(s) or until the change is no longer clinically relevant. In case of doubt, Novartis personnel should again be contacted.

6.5.4.1 Hematology

Hemoglobin, hematocrit, red blood cell count, white blood cell count with differential (e.g., neutrophils, basophils, eosinophils, monocytes, lymphocytes) and platelet count will be measured.

6.5.4.2 Clinical chemistry

Albumin, alkaline phosphatase, total bilirubin, bicarbonate/CO₂, calcium, cholesterol, chloride, creatinine, CK, γ -GT, glucose, LDH, inorganic phosphorus, lipase, amylase, magnesium, potassium, total protein, AST, ALT, sodium, triglycerides, BUN, and uric acid (for all laboratory assessments). Anti-Nuclear Antibody (ANA), anti-neutrophil cytoplasmic antibody (ANCA), rheumatoid factor, and anti-cyclic citrullinated peptides will be measured at screening only.

If the total bilirubin concentration is increased above 1.5 times the upper limit of normal, direct and indirect reacting bilirubin should be differentiated.

6.5.4.3 Urinalysis

A midstream urine sample (approx. 30 mL) will be obtained, in order to avoid contamination with epithelial cells and sediments, and allow proper assessments.

A semi-quantitative "dipstick" evaluation for the following parameters will be performed: specific gravity, pH, glucose, protein, bilirubin, ketones, nitrite, leukocytes and blood.

If the dipstick result is positive for protein, nitrite, leucocytes and/or blood, the sample will be sent for microscopic analysis of WBC, RBC and casts.

6.5.4.4 Special clinical laboratory evaluations

Not applicable.

6.5.5 Electrocardiogram (ECG)

A standard 12 lead ECG will be performed seated. Interpretation of the tracing must be made by a qualified physician and documented on the ECG / in the ECG section of the CRF. Each ECG tracing should be labeled with the

Confidential

- study number
- patient / patient initials
- patient / patient number
- date

and kept in the source documents at the study site. Clinically significant abnormalities should be recorded on the relevant medical history/Current medical conditions CRF page prior to informed consent signature and on the Adverse Events page thereafter. Clinically significant findings must be discussed with the sponsor.

The CRF will contain:

- date and time of ECG
- heart rate
- PR interval
- QT interval
- QTcF
- QRS duration

Original ECG tracings, appropriately signed, will be archived at study site.

6.5.6 Hearing and balance assessments

The assessments for efficacy outlined in Section 6.4 will also serve as safety assessments.

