5.5.8 Concomitant treatment

All prescription medications, over-the-counter drugs and significant non-drug therapies (including physical therapy and blood transfusions) administered or taken within the timeframe defined in the entry criteria prior to the start of the study and during the study, must be recorded on the Concomitant medications/ Significant non-drug therapies section of the CRF.

Confidential

Medication entries should be specific to trade name, the single dose and unit, the frequency and route of administration, the start and discontinuation date and the reason for therapy.

5.5.9 **Prohibited treatment**

Use of known ototoxins, for example systemic aminoglycoside antibiotics, should be avoided if possible following dose administration through study completions. If a known, potent ototoxin should be required, for example cisplatin, then the patient may remain in the study but should be excluded from the efficacy analysis.

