9.1 Analysis sets

For all analysis sets, patients will be analyzed according to the study treatment(s) received.

The safety analysis set will include all patients that received any study drug.

The PD analysis set will include all patients with available PD data and no protocol deviations with relevant impact on PD data.

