9.4.2 Statistical model, hypothesis, and method of analysis

Tone thresholds will be analyzed for each frequency tested separately.

For pure tone audiometry, a measure that depends on a patient being able to hear a tone, the following imputation will be done: If a patient is unable to hear the tone at a specific frequency it can be inferred that the threshold value exceeds the upper limit of the machine. In this case the value will be imputed to 5dB above the upper limit of the machine.

All pure tone audiometry air conduction threshold data will be listed and graphically displayed by patient, infusion volume, frequency, and visit/time. Summary statistics will be provided by infusion volume, frequency, ear and visit/time. Change from baseline of the thresholds (mean of screening and baseline visit) will also be summarized by infusion volume, frequency, ear and visit/time.

In addition, safety and tolerability is a co-primary endpoint, and will be analyzed as in Section 9.5.2 (Safety).

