9.5.2 Safety

Vital signs

All vital signs data will be listed by treatment, patient, and visit/time and if ranges are available abnormalities (and relevant orthostatic changes) will be flagged. Summary statistics will be provided by treatment and visit/time.

ECG evaluations

All ECG data will be listed by treatment, patient and visit/time, abnormalities will be flagged. Summary statistics will be provided by treatment and visit/time.

Clinical laboratory evaluations

All laboratory data will be listed by treatment, patient, and visit/time and if normal ranges are available abnormalities will be flagged. Summary statistics will be provided by treatment and visit/time.

Adverse events

All information obtained on adverse events will be displayed by treatment and patient.

The number and percentage of patients with adverse events will be tabulated by body system and preferred term with a breakdown by treatment. A patient with multiple adverse events within a body system is only counted once towards the total of this body system. Exact 95% binomial confidence intervals may be provided for AE rates. If a dose-related safety signal is suspected, this may be confirmed by a permutation contrast test t using the nominal dose level as contrast.

Confidential

Other safety evaluations

Not applicable.

Commercially Confidential Information

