2.2 Study design and treatment

The current three part study utilizes an open label, single dose design for the investigation of CGF166 and will be conducted in multiple centers. Part A, B and C will be conducted in a sequential manner.

The current study will evaluate the safety, tolerability, and potential efficacy of CGF166 and the associated delivery procedures in patients with severe-to-profound bilateral hearing loss with intact vestibular function in the non-operative ear. Patients are required to have documented non-fluctuating hearing loss.

Commercially Confidential Information

Part A

Part A will include a safety and tolerability cohort (N=3). Patient dosing will be staggered; dosing the next patient in a cohort will be based on a safety data review including all data available through 4 weeks post-dose of the previously dosed patient(s).

Part B

Part B will include a volumetric escalation design to evaluate infusion volumes of the same CGF166 concentration Commercially Confidential Information in 4 cohorts of patients (N=3/cohort; total of 12 patients).

Each subsequent cohort will be dosed only after the volume delivered in the prior cohort is deemed to be safe and tolerable as determined by the dose safety review meeting based on safety data review of the complete previous cohort including all data through 4 weeks post-dose.

Safety review meetings will be organized to evaluate available safety data and to determine if it is appropriate to escalate to the next infusion volume.

Part C

Once the highest safe and tolerable volume is determined in previous cohorts, it will be used for IL-infusion in Part C patients. A total of 20 patients, possibly increasing to 30 based on a sample size re-estimation after a data review of the Part A and B (cohorts 1-5), will be required for Part C of the current study.

3 First interpretable results (FIR)

Commercially Confidential Information

4 Interim analyses

Commercially Confidential Information

5 Statistical methods: Analysis sets

All patients that received study drug and with no protocol deviations with relevant impact on safety will be included in the safety analysis set.

Commercially Confidential Information

Commercially Confidential Information

6 Statistical methods for Pharmacokinetic (PK) parameters

Not applicable.

7 Statistical methods for Pharmacodynamic (PD) parameters

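### Hearing and balance tests are declared safety assessments, but the visible safety analysis contains none of them, and no analysis set is named for the threshold summaries

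*Protocol*

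**What the plan says.** **Status of the tests.** Protocol 6.5.6 states: "The assessments for efficacy outlined in Section 6.4 will also serve as safety assessments". Section 6.4 lists pure tone audiometry, speech audiometry, BAER and the head impulse test, and introduces them with "Efficacy/Pharmacodynamics will be measured in this clinical study by the following assessments".

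**Safety analysis.** Protocol 9.4.2 makes safety and tolerability co-primary and refers its analysis to 9.5.2. That section covers vital signs, ECG, laboratory data and adverse events. Its last visible heading, "Other safety evaluations", is answered as not applicable. SAP 8.1 covers the same four domains and adds MRI and the C-SSRS.

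**Threshold analysis.** Protocol 9.4.2 lists and plots all air-conduction thresholds by patient. It also summarises thresholds and change from baseline by infusion volume, frequency, ear and visit. The SAP treats thresholds in chapter 7, headed "Statistical methods for Pharmacodynamic (PD) parameters"; the visible 7.1.2 has listings and plots only. Neither document names the analysis set.

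**Sets and exclusions.** Protocol 9.1 gives two sets: "The safety analysis set will include all patients that received any study drug", and "The PD analysis set will include all patients with available PD data and no protocol deviations with relevant impact on PD data". Protocol 5.5.9 adds that if a potent ototoxin is required, "then the patient may remain in the study but should be excluded from the efficacy analysis". The visible SAP 5 definition of the safety set also requires that a dosed patient have no deviation relevant to safety.

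**The concern.** The product is infused into the inner ear, so loss of residual hearing or balance is an obvious harm to look for. Protocol 3.6.2 names worsened hearing as a surgical risk. Protocol 3.1 reports that audiometry changes were considered when 30 µL was endorsed as the maximum tolerated volume. Yet the analysis designated for the co-primary safety objective has no visible table of measured hearing or balance.

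The only summary of measured hearing sits on the efficacy/PD side, where stated rules can remove dosed patients. With cohorts of 3 and 10, one removal can change what a group summary shows. A reader of the safety results would have no all-dosed figure against which to check it.

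**Working it through.** The documents give no figure to reproduce here. The check is a comparison of text followed by an illustration.

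**Step 1: trace the tests to an analysis.**

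| Domain | Declared a safety assessment | In Protocol 9.5.2 | In visible SAP 8.1 |
|---|---|---|---|
| Vital signs, ECG, laboratory | yes | yes | yes |
| Adverse events | yes | yes | yes |
| MRI | yes (6.5.7) | no | yes |
| C-SSRS | yes (7.5) | no | yes |
| Section 6.4 hearing and balance tests | yes (6.5.6) | no | no |

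Only the last row has no entry in either safety analysis.

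**Step 2: who can be left out.** The protocol's safety set has no deviation filter, but no threshold summary is tied to it. The PD set has a filter, and 5.5.9 excludes potent-ototoxin users from efficacy. Which of these governs the thresholds is not stated.

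**Step 3: weight of one exclusion.** Planned sizes are 3 (Part A), 3 × 3 = 9 (Part B) and 10 (Part C), so 3 + 9 + 10 = 22, the stated maximum. One patient is 1/3 = 33% of a small cohort and 1/10 = 10% of Part C.

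Summaries are by infusion volume, and Protocol 5.2 gives cohort 2 as 40 or 30 µL. If cohorts are full and cohort 2 was split, the 40 µL group has 3 + 1 = 4 or 3 + 2 = 5 patients, and the 30 µL group has 10 + 2 = 12 or 10 + 1 = 11. One patient is then 20 to 25% of the former and 8.3 to 9.1% of the latter. The 20 and 60 µL groups stay at 3.

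**Step 4: illustration with counts.** Assume that one worsened ear is excluded. Exact 95% limits are the 0.025 quantile of Beta(x, n − x + 1) and the 0.975 quantile of Beta(x + 1, n − x). The lower limit is 0 when x = 0.

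| All dosed | After exclusion |
|---|---|
| 1/3 = 33% (0.8% to 90.6%) | 0/2 = 0% (0% to 84.2%) |
| 1/10 = 10% (0.3% to 44.5%) | 0/9 = 0% (0% to 33.6%) |
| 2/10 = 20% (2.5% to 55.6%) | 1/9 = 11.1% (0.3% to 48.2%) |

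**Step 5: illustration with means.** If one ear worsens by d dB and the others do not change, the mean is d/n and falls to 0 when that ear is removed. For an assumed d of 10 to 30 dB, the mean is 3.3 to 10 dB with n = 3 and 1 to 3 dB with n = 10. The documents give no expected d.

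**Step 6: why a mean or a dB cut-off is not enough.** A tone that is not heard is set to 5 dB above the machine limit L, so the largest recordable worsening at one frequency is L + 5 − b, where b is the baseline threshold. L is not given. An ear with b = L can show at most 5 dB, and any b from L − 5 to L shows at most 10 dB. Inclusion criterion 3 admits averages up to 110 dB HL. Ears that become unmeasurable therefore need their own count.

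**The case against.** The strongest reply has five parts.

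- **The set is inferred.** Nothing assigns thresholds to the PD set; the link is a section label and a chapter heading. All air-conduction data are to be listed and plotted by patient. The missing-data rules (Protocol 9.4.3, SAP 7.1.3) keep patients with partial data and exclude only those without any pre-treatment value, and only for change from baseline. In at most 22 patients a large loss would be seen. This stands, and it rules out reading the plan as certain to hide such a loss. It does not supply an all-dosed summary.
- **Other routes exist.** Under Protocol 7.1 a test result is an adverse event if it causes signs or symptoms, is clinically significant or needs therapy. The DSMB reviews audiometry and vestibular safety (8.4). This also stands, but the first route depends on judgement and the second is monitoring, not reported analysis.
- **Protocol 9.5.2 is not exhaustive.** MRI and the C-SSRS are missing there and appear in SAP 8.1. That is true, but hearing and balance appear in neither.
- **Redaction.** Blocks are removed after Protocol 9.5.2, after the SAP safety set and between MRI and the C-SSRS in SAP 8.1. Hidden SAP text may cover part of this. The not-applicable entry in the protocol is visible.
- **The 10 dB figure is an eligibility limit** for stability over at least 11 months, not a harm threshold. This stands, so the cut-off is for the sponsor to choose.

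A reader might also infer that any deviation removes a patient, that a faulty infusion would count as a PD-relevant deviation, or that exclusions will be decided with the audiograms in view. The documents support none of these. The PD filter is limited to deviations with relevant impact on PD data, no text classes infusion problems that way, and the visible text does not say who judges deviations or when. The trial is open label, but that alone does not establish the last inference.

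**Conclusion.** The conflict holds in visible text: tests declared to be safety assessments have no place in the analysis to which the co-primary safety endpoint is sent. It is a moderate point. The possible exclusion of a dosed patient with hearing loss depends on the PD set or the ototoxin rule being applied to the threshold summaries, which is plausible but unstated. If either is applied, one patient is a third of a cohort of 3 or a tenth of Part C, enough to take a single affected ear out of a group summary. The intervals in the illustration are wide with or without that patient, so what is at stake is complete description of harm, not a test result. To say that hearing loss would vanish from the trial's results goes too far, given the by-patient displays and the adverse event and DSMB routes.

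The SAP safety set is a separate, direct mismatch: its visible definition carries a deviation filter that Protocol 9.1 does not have.

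**What to change.** 1. In Protocol 9.5.2, replace the not-applicable entry, and add the same item to SAP 8.1: a descriptive summary by visit and infusion volume of study-ear threshold change from baseline and of the other Section 6.4 tests, including head impulse results, in all dosed patients regardless of deviations or ototoxin use.
2. Within it, count the study ears that worsened, using a cut-off that the sponsor fixes in advance. The 10 dB stability limit in inclusion criterion 2 is one option. Count separately the ears that newly become unmeasurable. Show denominators; exact intervals may be added, as 9.5.2 already allows for adverse event rates.
3. Name the analysis set for the threshold summaries in Protocol 9.4.2 and SAP 7.1.2. Keep the PD set for efficacy or sensitivity summaries.
4. Remove the deviation filter from the safety set in SAP 5 so that it matches Protocol 9.1.

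The cost is wording in both documents and a few tables from data already collected. The SAP needs a new version anyway: it still describes four Part B cohorts and 20 to 30 Part C patients, against three cohorts and 10 in the protocol. The hearing results may look slightly less favourable. If redacted SAP text already contains such a summary on all dosed patients, a cross-reference from Protocol 9.5.2 is enough for items 1 and 2.
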